1.2 ETHICS AND REGULATORY CONSIDERATIONS

The study will be conducted in compliance with the ethical principles that have their origin in the Declaration of Helsinki on biomedical research involving human volunteers (2013 Version), International Council for Harmonisation (ICH) of Technical Requirements for Pharmaceuticals for Human Use Guidelines for Good Clinical Practice (GCP), the study protocol, and where applicable, Sponsor and/or Contract Research Organization (CRO) Standard Operating Procedures (SOPs). The protocol and informed consent will be submitted for consideration by the appropriate Independent Review Board (IRB)/Independent Ethics Committee (IEC) and written approval from the Chair or designated deputy of the IRB/IEC is required before clinical activities of the study can commence.

The IRB/IEC must be notified promptly by the Investigator of the following:

- Deviations from, or changes in, the protocol to eliminate immediate hazards to the study subjects
- Changes increasing the risk to subjects and/or significantly affecting the conduct of the study
- All AEs that meet the definition of an SAE
- New information that may affect adversely the safety of the subjects or the conduct of the study

Any changes to the protocol will be made by means of a formal written protocol amendment. All amendments will require IRB/IEC approval before implementation, except when changes to the protocol are required immediately to eliminate hazards to the subjects.

2 STUDY OBJECTIVES

2.1 PRIMARY OBJECTIVE

To evaluate the long-term safety and tolerability of ralinepag in subjects with WHO Group 1 PAH who have completed Study APD811-003.

2.2 SECONDARY OBJECTIVES

- To evaluate the effect of ralinepag in subjects with WHO Group 1 PAH who completed Study APD811-003, as determined by the incidence of clinical worsening.
- To evaluate changes from baseline in the following efficacy endpoints:
 - 6MWD
 - WHO/NYHA FC
 - Hemodynamics

3 INVESTIGATIONAL PLAN

3.1 OVERALL STUDY DESIGN AND PLAN

This is a Phase 2, multicenter, open-label, extension study to determine the long-term safety and tolerability of ralinepag in subjects with WHO Group 1 PAH who have completed the Phase 2 study, APD811-003, or who were assigned to placebo and were discontinued for clinical worsening. Subjects must also meet eligibility criteria for participation in this long-term extension study. The Day 1 (Baseline) visit in Study APD811-007 will coincide with the Week 25 Visit in Study APD811-003. For this reason, subjects should be consented to Study

APD811-007 prior to the Week 25 procedures being performed for Study APD811-003. Baseline/Day 1 evaluations will include medical history update, assessment of disease state, and determination of eligibility for each potential subject.

All subjects enrolled in Study APD811-007 will receive open-label treatment with ralinepag. The starting dose and titration schedule will be individually determined in accordance with the starting dose and titration schedule optimized from Study APD811-003. Adjustments in the dose and titration schedule may be made according to subject tolerability. After the completion of Study APD811-003, ongoing safety review of subject data will be conducted by the Sponsor to monitor for drug safety.

After an individual subject completes Study APD811-003 and that subject's database is locked, subject unblinding will occur. Subjects who were on active treatment (ralinepag) in Study APD811-003 will remain on current dose and have onsite clinical assessments performed every 3 months until the subject is discontinued from the study (see Table 1).

Subjects in the placebo treatment group of Study APD811-003 will undergo a Dose Titration Period until a stable maximum tolerated dose (MTD) is reached (up to 9 weeks); this will be followed by a Treatment Period in which monthly onsite clinic assessments will be performed for the first 3 months and then every 3 months until the subject is discontinued from the study or the study is terminated (see Table 2).

Subjects will continue to have visits to the clinic every 3 months indefinitely to collect data as specified in Table 1 and Table 2 until marketing approval of ralinepag is granted or until the Sponsor discontinues the study.

During the conduct of the study, subjects will switch from the IR formulation of ralinepag (as studied in ADP811-003) to an XR formulation that will be used in Phase 3 studies.

For both IR and XR formulations, dose reductions may be made at any time for safety/tolerability reasons. Incremental dose increases will also be allowed during the Treatment Period (Table 1 and Table 2) at the discretion of the Investigator (as clinically indicated) and according to the stepwise titration scheme outlined in Table 4.

Subjects will be assessed for clinical worsening during each clinic visit. If clinical worsening is confirmed, the Investigator may opt to either continue treatment with ralinepag at the current dose, increase the dose of ralinepag, interrupt treatment, or discontinue the subject at his/her discretion. Addition/dose increases/substitutions of 1 drug within the ERA class and 1 within the PDE5-I/soluble guanylate cyclase (sGC) stimulator class are also permissible.

In addition, all subjects will be contacted at the time of Study APD811-007 closure to assess vital (mortality) status. The vital status follow-up contact of subjects will depend on local regulations or specific agreement with the subject and Investigator.

Upon termination of the study, subjects will complete an End of Study Visit. A 28-day Follow-up Visit will be conducted to ensure appropriate subject safety. This visit may be conducted by telephone or in person based upon the Investigator's discretion. Subjects who remain on ralinepag at study termination and meet all eligibility criteria are eligible to roll into the open-label extension study (ROR-PH-303).

Concomitant Medications:

Subjects are permitted oral disease-specific PAH therapy consisting of an ERA and/or a PDE5-I or sGC stimulator, but not both. The on-study addition/substitution of an ERA, PDE5-I/sGC stimulator, if on a single such agent at Baseline, or dosage increase for such agents is permitted. In addition to ralinepag, subjects can be prescribed no more than 1 agent from the ERA class and 1 from the PDE5-I/sGC stimulator class at any 1 time. Substitution and dose adjustment within each of these classes is permitted. Subjects should be evaluated for the presence of clinical worsening if additional therapy or dose adjustments/substitutions of current therapies are required.

In addition, the following therapies, which may affect PAH, are permitted and may be adjusted in dose as needed:

- Vasodilators (including calcium channel blockers)
- Digoxin
- Spironolactone
- L-Arginine supplementation

Diuretics may be dosed as clinically indicated throughout the study.

Subjects who require treatment with a prostacyclin/prostacyclin analogue (IV, SC, oral, or inhaled), except for acute vasodilator testing during cardiac catheterization, will be discontinued from the study.

3.2 RATIONALE FOR STUDY DESIGN

This study is designed to evaluate the long-term safety and tolerability of ralinepag in subjects with PAH.

Inclusion of a placebo arm in Study APD811-003 and the requirement to maintain the blind in that study necessitates the re-titration of all subjects entering Study APD811-007. Thus, the dose titration scheme from Study APD811-003 will be employed in this study for subjects who were previously treated with placebo in Study APD811-003.

Optimal dosing of IP receptor agonists in PAH subjects requires dose titration on an individualized basis; furthermore, tolerability may improve with continued exposure.¹⁵ It is anticipated that the starting dose of 10 mcg BID will be tolerated by most, if not all, subjects. Data from the previous Phase 1 dose titration study suggests that there are individual differences in tolerability of ralinepag in healthy volunteers, consistent with findings from other studies of prostacyclin receptor agonists in PAH subjects.

Table 1 Schedule of Procedures and Visits: Study APD811-003 Subjects Treated with Ralinepag Entering Study APD811-007

Evaluation ^a	Baseline ^b (APD811-003 Week 25 Visit)	Treatment Period		End of Study (EOS)	28-Day Follow-Up ^c
		Q3 Months	1 or 2 Years		
		±5 days	±3 months	±3 days	±3 days
Informed consent	X				
Medical history	X				
Physical exam	X			X	
ECG (12-lead) ^d	X	X		X	
Clinical laboratory tests ^e	X	X		X	
Pregnancy test ^f	X	X		X	
Vital signs ^g	X	X		X	
Study drug administration	X ^h	X			
6MWT	X	X		X	
BNP/NT-proBNP ^k	X	X			
Assessment of clinical worsening	X	X		X	X
WHO/NYHA FC assessment ⁱ	X	X		X	X
RHC ^l			X		
Dose escalation/de-escalation assessment		X ^j			
Adverse event monitoring	X	X		X	X
Concomitant medication monitoring	X	X		X	X

Abbreviations: 6MWT, 6-Minute Walk Test; BNP, brain natriuretic peptide; ECG, electrocardiogram; FC, Functional Class; hCG, human chorionic gonadotropin; NT-proBNP, N-terminal pro-brain natriuretic peptide; NYHA, New York Heart Association; Q3, every 3; QTcB, QT interval corrected for Bazett’s formula; QTcF, QT interval corrected for Fridericia’s formula; RHC, right heart catheterization; RR, respiration rate; WHO, World Health Organization

^a Reference to pre-dose and post-dose activities in this schedule apply to the morning dose of study drug. Study drug should be taken with food.

^b The Week 25 (Day 175) Visit from Study APD811-003 will serve as the Baseline/Day 1 Visit for Study APD811-007.

^c This visit may be conducted by telephone or in person based upon the Investigator’s discretion.

^d Safety ECGs should be completed pre-dose. After the last subject enrolled in Study APD811-007 completes approximately 6 months of treatment and a cumulative all-subject data analysis is performed, as outlined in Section 9 (Planned Statistical Methods), ECGs will subsequently be conducted locally at the discretion of the

- Investigator (as clinically indicated) during the Q3 monthly visits. The ECG will be performed at the End of Study Visit. Locally collected ECG values for RR, PR, QRS, QT, QTc, QTcB, and QTcF will be collected in the Sponsor's clinical database.
- ^e Clinical laboratory tests will include hematology, serum chemistry, coagulation, and urinalysis. Clinical laboratory tests will be completed pre-dose. After the last subject enrolled in Study APD811-007 completes approximately 6 months of treatment and a cumulative all-subject data analysis is performed, as outlined in Section 9, clinical laboratory tests will subsequently be conducted locally at the discretion of the Investigator (as clinically indicated) during the Q3 monthly visits. A complete clinical laboratory test will be conducted locally at the End of Study Visit. Locally collected laboratory values that are abnormal and clinically significant will be collected in the Sponsor's clinical database along with the reference ranges.
 - ^f Serum hCG pregnancy tests will be completed pre-dose at each visit during the Treatment Period. After the last subject enrolled in Study APD811-007 completes approximately 6 months of treatment and a cumulative all-subject data analysis is performed, as outlined in Section 9, pregnancy testing (either serum or urine) will subsequently be conducted locally during each Q3 monthly and the End of Study Visit. Locally collected positive values for hCG will be collected in the Sponsor's clinical database along with the reference range.
 - ^g Vital sign measurements (blood pressure, heart rate, respirations, and body temperature taken in supine position after 5 minutes of rest) will be taken pre-dose.
 - ^h Subjects treated with ralinepag in Study APD811-003 study will continue on current dose.
 - ⁱ WHO/NYHA Functional Class will be assessed pre-dose at all visits.
 - ^j An assessment for further dose escalation or de-escalation will be conducted during the Q3 months.
 - ^k After the last subject enrolled in Study APD811-007 completes approximately 6 months of treatment and a cumulative all-subject data analysis is performed, as outlined in Section 9 (Planned Statistical Methods), pro-BNP and NT-proBNP testing will subsequently be conducted locally at the discretion of the Investigator (as clinically indicated) during the Q3 monthly visits. Locally collected values will be entered into the Sponsor's clinical database along with the reference ranges.
 - ^l At 1 year (± 3 months) after the subject enrolls into Study APD811-007, an RHC assessment will be conducted. If the subject has been in Study APD811-007 beyond 1 year (± 3 months) at the time of regulatory/ethics approval of this amendment, an RHC assessment will be conducted at 2 years (± 3 months) instead. If a subject has been enrolled in Study APD811-007 more than 2 years at the time of regulatory/ethics approval of Amendment #02, an RHC will be performed at the time of those approvals.

Table 2 Schedule of Procedures and Visits: Study APD811-003 Subjects treated with Placebo entering Study APD811-007

Evaluation ^a	Baseline ^b (APD811-003 Follow-up Visit)	Dose Titration Period									Treatment Period			End of Study (EOS)	28-Day Follow- Up ^c
		9-Week Period									M1-M3	Q3 Months	1 or 2 Years		
		1	2	3	4	5	6	7	8	9	±3 days	±5 days	±3 months		
Informed consent	X														
Medical history	X														
Physical exam	X													X	
ECG (12-lead) ^d	X	X	X	X	X	X	X	X	X	X	X	X		X	
Clinical laboratory tests ^e	X		X			X				X	X	X		X	
Serum pregnancy test ^f	X					X					X	X		X	
Vital signs ^g	X	X	X	X	X	X	X	X	X	X	X	X		X	
Study drug administration		X	X	X	X	X	X	X	X	X	X	X			
6MWT ^h	X										X	X		X	
BNP/NT-proBNP ^k	X											X			
WHO/NYHA functional class assessment ⁱ	X	X	X	X	X	X	X	X	X	X	X	X		X	X
Assessment for clinical worsening	X	X	X	X	X	X	X	X	X	X	X	X		X	X
RHC ^l													X		
Dose escalation/de-escalation assessment												X ^j			
Adverse event monitoring	X	X	X	X	X	X	X	X	X	X	X	X		X	X
Concomitant medication monitoring	X	X	X	X	X	X	X	X	X	X	X	X		X	X

Abbreviations: 6MWT, 6-Minute Walk Test; BNP, brain natriuretic peptide; ECG, electrocardiogram; hCG, human chorionic gonadotropin; MTD, maximum tolerated dose; NT-proBNP, N-terminal pro-brain natriuretic peptide; NYHA, New York Heart Association; Q3, every 3; QTcB, QT interval corrected for Bazett’s formula; QTcF, QT interval corrected for Fridericia’s formula; RHC, right heart catheterization; RR, respiratory rate; WHO, World Health Organization

^a Reference to pre-dose and post-dose activities in this schedule apply to the morning dose of study drug. Study drug should be taken with food.

^b The Week 25 Visit from Study APD811-003 will serve as the Baseline/Day 1 Visit for Study APD811-007.

- ^c This visit may be conducted by telephone or in person based upon the Investigator's discretion.
- ^d Safety ECG measurements to be completed at Baseline and at Weeks 1 to 9, unless the subject reaches a stable MTD and the subject transitions into the Treatment Period; ECGs will be completed pre-dose and 2 hours post-dose. After the last subject enrolled in Study APD811-007 completes approximately 6 months of treatment and a cumulative all-subject data analysis is performed, as outlined in Section 9, ECGs will subsequently be conducted locally at the discretion of the Investigator (as clinically indicated) during the Q3 monthly visits. The ECG will be performed at the End of Study Visit. Locally collected ECG values for RR, PR, QRS, QT, QTc, QTcB, and QTcF will be collected in the Sponsor's clinical database.
- ^e Clinical laboratory tests will include hematology, serum chemistry, coagulation, and urinalysis. Clinical laboratory tests will be completed pre-dose. After the last subject enrolled in Study APD811-007 completes approximately 6 months of treatment and a cumulative all-subject data analysis is performed, as outlined in Section 9, clinical laboratory tests will subsequently be conducted locally at the discretion of the Investigator (as clinically indicated) during the Q3 monthly visits. A complete clinical laboratory test will be conducted locally at the End of Study Visit. Locally collected laboratory values that are abnormal and clinically significant will be collected in the Sponsor's clinical database along with the reference ranges.
- ^f Serum pregnancy test will be completed pre-dose at each visit during the Treatment Period. After the last subject enrolled in Study APD811-007 completes approximately 6 months of treatment and a cumulative all-subject data analysis is performed, as outlined in Section 9 (Planned Statistical Methods), pregnancy testing (either serum or urine) will subsequently be conducted locally during each Q3 monthly and the End of Study Visit. Locally collected positive values for hCG will be collected in the Sponsor's clinical database along with the reference range.
- ^g Vital sign measurements (blood pressure, heart rate, respirations, body temperature, and pulse oximetry [SpO₂]), taken in supine position after 5 minutes of rest) will be taken at pre-dose on Day 1, and pre-dose on the first day of each dose increase. On the first day of each dose increase, blood pressure and heart rate will be taken approximately every hour for the first 4 hours after study drug administration. Vital signs will be measured prior to any blood draw that occurs at the same time point.
- ^h The 6MWT should be completed pre-dose at approximately the same time of day at each designated visit.
- ⁱ WHO/NYHA Functional Class will be assessed pre-dose at all visits.
- ^j An assessment for further dose escalation or de-escalation will be conducted during the Q3 months.
- ^k After the last subject enrolled in Study APD811-007 completes approximately 6 months of treatment and a cumulative all-subject data analysis is performed, as outlined in Section 9, pro-BNP and NT-proBNP testing will subsequently be conducted locally at the discretion of the Investigator (as clinically indicated) during the Q3 monthly visits. Locally collected values will be entered into the Sponsor's clinical database along with the reference ranges.
- ^l At 1 year (± 3 months) after the subject enrolls into Study APD811-007, an RHC assessment will be conducted. If the subject has been in Study APD811-007 beyond 1 year (± 3 months) at the time of regulatory/ethics approval of Amendment 2, an RHC assessment will be conducted at 2 years (± 3 months) instead. If a subject has been enrolled in Study APD811-007 more than 2 years at the time of regulatory/ethics approval of Amendment 2, an RHC will be performed at the time of those approvals.

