6.10 CLINICAL LABORATORY TESTS

All details regarding clinical laboratory sample collection, preparation, and shipment are included in the laboratory manual provided by the central laboratory for visits that require centralized lab collection (see Table 1 and Table 2).

In the event of abnormal clinical laboratory values, the physician will make a judgment whether or not the abnormality is clinically significant.

After the last subject enrolled in APD811-007 completes approximately 6 months of treatment and a cumulative all-subject data analysis is performed, as outlined in Section 9, clinical laboratory tests will subsequently be conducted locally at the discretion of the Investigator (as clinically indicated) during the Q3 monthly visits. Locally collected laboratory values that are abnormal and clinically significant will be collected in Sponsor’s clinical database along with the reference ranges.

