8 DATA MANAGEMENT

8.1 DATA COLLECTION

All data (ECGs, clinical laboratory data, and all other study-related data) will be collected according to the Sponsor or CRO's SOPs.

Upon database lock, to include resolution of all queries, the CRO (if applicable) will provide statistical analysis software transfer datasets to the Sponsor and biostatistician for analysis using secure electronic data transfer per the Sponsor's specifications.

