9.2.1.5 Clinical Laboratory Values

Individual laboratory values will be listed by visit and summarized using descriptive statistics. Summary statistics will also be provided for change from Baseline in laboratory values. Shift tables from baseline to the last extension study visit will also be produced for the laboratory assessments based on the categories of Low, Normal, and High. A clinically significant change from baseline may be recorded as an AE if deemed appropriate by the Investigator or Sponsor.

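### After the switch to local laboratory testing, only abnormal, clinically significant values are named for database entry, and SAP 11.3 has no rule to keep such values out of the by-visit and shift tables

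*Protocol*

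**What the plan says.** **Protocol, after the cumulative analysis.** Section 6.10 states that "clinical laboratory tests will subsequently be conducted locally at the discretion of the Investigator (as clinically indicated) during the Q3 monthly visits". Footnote e of Tables 1 and 2 says the same and adds: "A complete clinical laboratory test will be conducted locally at the End of Study Visit". In all three places the entry rule reads "Locally collected laboratory values that are abnormal and clinically significant will be collected in" the Sponsor's clinical database, with reference ranges. Section 6.10 makes clinical significance a separate judgement: "In the event of abnormal clinical laboratory values, the physician will make a judgment whether or not the abnormality is clinically significant".

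**Other local measurements.** ECG intervals carry no filter on the result: "Locally collected ECG values for RR, PR, QRS, QT, QTc, QTcB, and QTcF will be collected in the" Sponsor's database (Table 1, footnote d). Nor do BNP and NT-proBNP: "Locally collected values will be entered into the" same database (footnote k).

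**Planned laboratory analysis.** Protocol 9.2.1.5 says: "Shift tables from baseline to the last extension study visit will also be produced for the laboratory assessments". SAP 7 uses all available data and SAP 8.2 imputes nothing. SAP 11.3 plans values and changes at each analysis visit for hematology, chemistry and coagulation, urinalysis category percentages at all analysis visits, and hematology and chemistry shift tables. It does not mention sample source. SAP 12 comments on local results only for BNP/NT-proBNP, which it reports as unavailable.

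**The concern.** Before the switch, a by-visit summary describes everyone tested at that visit. After it, a local result has to pass two filters before it can enter a summary: the investigator chose to test, and the result was abnormal and judged clinically significant. At End of Study the panel is mandatory, so only the second filter applies, but no rule says that its normal results are entered.

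A row made up only of local values would be so sparse that a reader would notice. A row mixing complete central values with filtered local ones would not show the selection. Such rows can arise because subjects are at different visits when the switch takes effect, and SAP 8.4 usually summarises by nominal visit without windows.

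Laboratory parameters are a listed safety endpoint (SAP 2.2). What is at stake is whether the later rows and the shift tables describe the treated subjects or only those with a notable abnormality.

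**Working it through.** The documents give no figure to reproduce and no local data rates, so this is an illustration and not an estimate.

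**From the documents:** about 60 subjects (Protocol synopsis), the entry rule, and the SAP summaries (mean, SD, median, minimum, maximum; SAP 8).

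**Assumed:** a normally distributed analyte in SD units; reference limits at ±1.96; no true change; testing unrelated to the result; entry only beyond a cut-off c. Let f be the local share of a row and t the share of local subjects tested. I use c = 2.5 because the filter is narrower than out of range. c = 1.96 with everyone tested is an upper bound.

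**1. Selected values per analyte in a 60-subject mixed row.** Formula: 60 × f × t × p, with p = 2(1 − Φ(c)) = 0.01242 at c = 2.5.
- f = 0.5, t = 0.25: 60 × 0.5 × 0.25 × 0.01242 = 0.09
- f = 0.9, t = 1: 60 × 0.9 × 1 × 0.01242 = 0.67
- Upper bound (c = 1.96, p = 0.05, f = 0.9, t = 1): 2.7

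**2. Spread (true SD 1), entry in both tails.** SD = √{[(1 − f) + f·t·p·(1 + c·φ(c)/(1 − Φ(c)))] / [(1 − f) + f·t·p]}. At c = 2.5 the bracketed factor is 1 + 2.5 × 0.01753/0.00621 = 8.06. For f = 0.9, t = 1: √(0.1901/0.1112) = 1.31.

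**3. Mean.** With symmetric entry the bias is zero. If only high values are entered, bias = f·t·φ(c) / [(1 − f) + f·t·(1 − Φ(c))]. For c = 2.5, f = 0.9, t = 1: 0.01578/0.1056 = 0.15.

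| Scenario | f = 0.5 | f = 0.75 | f = 0.9 |
|---|---|---|---|
| SD, c = 2.5, t = 0.25 | 1.01 | 1.03 | 1.09 |
| SD, c = 2.5, t = 1 | 1.04 | 1.12 | 1.31 |
| SD, upper bound | 1.10 | 1.26 | 1.56 |
| Mean bias (SD), c = 2.5, t = 0.25 | 0.004 | 0.013 | 0.039 |
| Mean bias (SD), c = 2.5, t = 1 | 0.02 | 0.05 | 0.15 |
| Mean bias (SD), upper bound | 0.06 | 0.16 | 0.43 |

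Q3-month testing is discretionary, so t = 0.25 may be nearer for those rows. t = 1 fits only the End of Study panel.

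**4. Shifts, normal to abnormal, as a share of subjects normal at baseline.** Simulation of 2,000,000 subjects with equal correlation between visits, one central post-baseline value, then four local visits.

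| Rule for the last value (correlation 0.7; true rate 3.5%) | Result |
|---|---|
| Last recorded value, c = 2.5, t = 0.25 | 3.9% |
| Last recorded value, c = 2.5, t = 0.25 at three visits, then all at End of Study | 4.2% |
| Last recorded value, c = 2.5, t = 1 | 5.0% |
| Last recorded value, c = 1.96, t = 1 (upper bound) | 12.0% |
| Value at the last visit only, c = 2.5, t = 1 | 0.6% |

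With the last recorded value and c = 2.5, correlation 0.9 gives about 2.2 to 2.4% against a true 2.1%; correlation 0.5 gives about 5.0 to 7.1% against 4.3%. Neither document says which last-value rule applies, and the two rules err in opposite directions.

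**The case against.** The strongest objection is that bias needs three facts the documents do not establish: that normal local results were not entered, that the filtered ones reached the final dataset, and that they are pooled with central values. The protocol names what is to be entered but does not forbid the rest. Section 8.1 defers to procedures not supplied: "All data (ECGs, clinical laboratory data, and all other study-related data) will be collected according to the Sponsor or" CRO's SOPs. SAP 12 reports local BNP/NT-proBNP as unavailable although the protocol required their entry, so protocol wording is a poor guide to what was captured. This stands, and it makes the point conditional. It does not close the gap: if no local laboratory values exist, SAP 12 should say so, as it does for BNP; if they exist, a rule is needed.

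A second objection is that the effect is small and the tables are descriptive. This also stands. SAP 11.3 plans no by-visit percentage abnormal for hematology, chemistry or coagulation, so an inflated percentage is the wrong measure for them. With t = 0.25 and c = 2.5, about 85 to 91% of mixed rows would hold no selected value for a given analyte. The listings carry reference ranges and low/high flags, and Protocol 9.2.1.5 allows a clinically significant change to be recorded as an AE.

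Third, a single clarifying sentence in SAP 12 might be enough. That is the right first step, but if filtered values were captured, the tables still need a rule.

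**Conclusion.** The point holds as a minor, conditional one. The protocol's entry rule selects local laboratory values by their result, and the SAP has no provision to keep such values out of summaries meant for complete data. If they were captured and are pooled as written, spread and extremes are inflated, and means move if the abnormalities are mostly one-sided: about 0.004 to 0.15 SD at the 2.5 SD cut-off, with 0.43 SD as an upper bound. Shifts may come out too high or too low, depending on the unstated last-value rule. All sizes rest on the assumptions above. Testing prompted by symptoms could raise the counts, but the documents give no rate.

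A reader might infer that the final laboratory tables are biased towards abnormality, or that the safety conclusions are compromised. The documents support neither. They do not show which local values were entered. They give no switch date, and SAP 5 does not say that the September 2018 interim was the analysis that triggers the switch. The primary outcome measures are AEs and SAEs, whose tables are unaffected, as are pre-switch laboratory visits. The 12.0% shift should be read only as an upper bound, because it assumes that every out-of-range value is entered and every subject is tested at all four local visits.

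**What to change.** 1. In SAP 12, state which local laboratory data were captured (none, filtered, or all) and the date of the switch.
2. In SAP 11.3, limit by-visit values, changes, urinalysis percentages and shift tables to centrally analysed samples, and label shifts as running to the last central visit. Show the local End of Study panel as a separate labelled row only if all its results, normal and abnormal, were entered.
3. Add a central/local flag to the existing laboratory listings.
4. Report local clinically significant abnormal values separately, as the number of subjects with at least one, beside the number on treatment and, if captured, the number tested. Note that a percentage of those on treatment is a lower bound because testing was discretionary.

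The cost is a few lines of SAP text and one programming flag. The downside is that laboratory means and shifts stop at the last central visit unless the End of Study panel was fully entered. That departs from Protocol 9.2.1.5 and should be listed as such in SAP 12.
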